3.5. Study Flowchart

Figure 2. Study Flowchart

3.6 Study Procedures

This will be a single-arm unblinded trial evaluating the safety and efficacy and effects of HCV eradication with Viekira Pak or Mavyret on kidney function and markers of CKD progression.

Initial Screening Period

Patients will be asked to perform two screening visits. At the first visit they will be screened for eligibility according to the above inclusion and exclusion criteria. They will also have screening blood and urine tests performed. Patients will undergo Fibroscan to determine the degree of cirrhosis unless they have a prior biopsy documenting cirrhosis. At this visit they will undergo informed consent and participant and investigators will each receive a copy of the signed consent form. The primary purpose of the second screening visit is to establish a stable baseline level of renal function including cystatin C and creatinine based estimated GFR estimate and proteinuria level.

Baseline Visit

At the baseline visit, patients will undergo full medical history and physical examination, ECG monitoring, quality of life assessment with SF36 and FACIT-F (a fatigue scale). Patients will undergo venous sampling for routine bloodwork and sampling of blood and urine for study assays (**Table 1a and 1b**). Patients will receive the first four weeks of study drug at the baseline visit.

Table 1a. Traditional Markers of CKD Progression

Measured at Baseline, Week 4, Week 8, Week 12 or 16 (if needed), SVR4, SVR12, SVR24 and 1 year

Serum creatinine (mg/dL)
Serum cystatin C (mg/L)
Urine total protein (mg/dl) / urine creatinine (mg/dl) ratio
Urine albumin (mg/dl) / urine creatinine (mg/dl) ratio
White blood cell differential – monocyte count linked to CKD progression and atherosclerosis ^[23]

Table 1b. Novel Markers of CKD Progression
Measured at Baseline, Week 8, SVR12, and 1 year follow-up

Serum FGF-23– validated marker of incident and progressive CKD ^[24]
Serum CRP – marker of incident and progressive renal failure ^[25, 26]
Serum and Urine IL-6 - marker of incident and progressive renal failure ^[25, 26]
TNF-alpha receptor - marker of incident renal failure ^[26]
Soluble CD163 – liver fibrosis, marker of macrophage activity, implicated in mechanism of immune complex kidney disease ^[27]
Urine neutrophil gelatinase associated lipocalin (NGAL) – correlates with more advanced fibrosis on kidney biopsy ^[28] and with incident CKD ^[29] and cardiovascular mortality in CKD ^[30] .

Dosing regimen

Patients will be prescribed DAA therapy (Viekira Pak or Mavyret) based on current standard of care. We will submit the prescription for approval by their insurance company. If insurance approval is denied, or if the patient is uninsured, the treatment course will be provided by Abbvie.

On label use of the Viekira or Mavyret regimen will follow recommendations provided by the AASLD and IDSA, (HCVguidelines.org, accessed 10/11/17).

Patient receiving Mavyret:

1. Genotype 1-6 noncirrhotic, treatment naïve patients will receive 8 weeks of Mavyret
2. Genotype 1-6 with cirrhosis, treatment naïve patients will receive 12 weeks of Mavyret
3. Genotype 1, 2, 4, 5, 6 patients treatment experienced with either interferon, ribavirin, sofosbuvir, or a protease inhibitor will receive 12 weeks of Mavyret
4. Genotype 3 patients that are treatment experienced with either interferon and/or ribavirin will receive 16 weeks of Mavyret

Patients receiving Viekira-Pak based regimens:

Genotype 1a - Paritaprevir (150mg)/ritonavir (100mg)/ombitasvir (25mg), once daily, dasabuvir (250mg) twice daily, ribavirin 200mg-400mg daily (based on eGFR) for 12 weeks. Excluded if cirrhotic.

Genotype 1b. Paritaprevir (150mg)/ritonavir (100mg)/ombitasvir (25mg) once daily, dasabuvir (250mg) twice daily for 12 weeks. Ribavirin 200mg daily added if there is a history of cirrhosis. Initial Ribavirin dosing will follow package insert and begin with 200mg daily for patients with $<30\text{mL}/\text{min}/1.73\text{m}^2$. Dose adjustments for anemia will follow published guidelines.[30]

Genotype 4 – Paritaprevir (150mg)/ritonavir(100mg)/ombitasvir (25mg) once daily and ribavirin 200-400mg (based on eGFR) once daily for 12 weeks.

On-Treatment Follow-up visits – Treatment period will be based on standard of care for all subjects
Patients will undergo a follow-up visit at 2 weeks, 4 weeks, 8 weeks and 12 and 16 weeks if needed on therapy and monitoring for adverse events by the study investigators with history and targeted physical exam and with routine bloodwork will occur at every study visit. Routine 12 lead ECG will be monitored on week 2 and end of treatment. Quality of life measures will be taken at 8 weeks on therapy. Traditional CKD biomarkers (**Table 1a**) will be measured at week 4, 8, and 12. Novel biomarkers (**Table 1b**) will be measured at week 8 on treatment.

Post-Treatment Follow-up Visits

Patients will undergo four post-treatment follow-up visits at SVR4 (4 weeks after treatment ends) SVR12 (12 weeks after treatment ends), SVR24 (24 weeks after treatment ends) and 1 year follow-up (day 365). Kidney function tests and novel biomarker analysis will be assessed at each of these visits. AEs will be recorded at SVR4 and the study investigator will determine if it is treatment-related or not. Quality of life assessments (SF36 and FACIT-F) will be measured at SVR12 and 1 year visit. Traditional CKD biomarkers (**Table 1a**) will be measured at all follow-up visits. Novel biomarkers (**Table 1b**) will be measured at SVR12 and 1 year follow-up.

Withdrawal Criteria

Patients will be monitored carefully for any side effects or adverse events. Serum laboratory results will be monitored at every study visit. [name] will review results. If indicated, subjects may be asked to visit more frequently for monitoring if any abnormalities are found. If at any time adverse effects are experienced by the subjects, they will have 24-hour access to speak with a member of the study staff, we will immediately provide the appropriate medical and professional intervention. At any time, [name] and [name] have the right to withdraw patients due to concurrent illness, adverse events, or treatment failure. These conditions are include: 1) Pregnancy of female subject 2) Efficacy/Virologic Failure (defined below) and 3) Significant adverse event requiring termination of study drugs 4) [name] and [name] feel it's in the best interest of the patient to stop study participation for medical safety 5) If the study is stopped by the, IRB or the FDA the patient will be removed from the protocol and followed for safety reasons only. If a subject is withdrawn prior to receiving the first study medication dose then they will be replaced. If a subject is withdrawn from the trial after receiving ≥ 1 dose of study medication then they will not be replaced. Patients who are withdrawn from the trial treatment will still undergo visits at all scheduled follow-up time-points up until 1 year as originally planned.

Virologic Failure Study Withdrawal Criteria

- Confirmed HCV RNA \geq LLOQ after 2 consecutive HCV RNA $<$ LLOQ
- Confirmed $> 1 \log_{10}$ increase from nadir
- HCV RNA \geq LLOQ through 8 weeks of treatment

Drs [name] and [name] will serve as the data safety monitoring board (DSMB). Once 1/3 of the subjects have been enrolled and again after 2/3 of subjects have enrolled, the [name] and [name] will meet and can stop the study based on the safety of therapy.

Safety will be evaluated by clinical laboratory tests, physical exam, vital signs measurements and by the documentation of AEs. Clinical and laboratory AEs will be coded using the Medical Dictionary for Regulatory Activities. A treatment-emergent adverse event will be defined as any new or worsening adverse event that begins on or after the date of first dose of study drug up to the date of last dose of study drug plus 30 days.

Summaries of treatment-emergent adverse events will be provided for the following (1) All AEs (2) All study drug-related AEs (3) All grade 3, 4 AEs (4) All study drug-related grade 3, 4 AEs (5) All AEs leading to permanent discontinuation of the study drug (6) All SAEs (7) All study drug related SAEs. Pertinent laboratory data will be summarized and corresponding change from Baseline/Day 1 will be presented throughout the study period. Graded laboratory abnormalities will be defined using the standard WHO laboratory toxicity grading.

To evaluate the safety and tolerability of each treatment regimen as assessed by review of the accumulated safety data by determining the number of adverse events leading to discontinuation of the regimen. Treatment-emergent data will be analyzed and defined as data collected from the first dose of study drug through the date of last dose of study drug plus 30 days.

Publication Plan

Presentation at Conferences:

Presentation of preliminary results at AASLD 2018

Presentation of renal biomarker results at American Society of Nephrology 11/2019

Manuscript:

Publication in Hepatology or Journal of the American Society of Nephrology - Submission December 2019

3.7 Statistical Analysis and Sample Size Justification

Statistical analysis: Summary statistics of baseline characteristics for all patients will be described. Demographic and baseline characteristics will be summarized using standard descriptive methods and will include age, sex, and self-identified race/ethnicity. Baseline characteristic data will include body mass index, HCV RNA level (log₁₀ IU/mL), genotype HCV infection, and additional comorbidities (cirrhosis, diabetes, hypertension, HIV infection). The number (proportion of subjects) in each genotype stratum and response to prior HCV therapy will be summarized.

With N = 10 patients included we conservatively estimate that at least 9 will achieve SVR. With 10 patients each with 4 measurements of novel and traditional kidney and cardiovascular risk biomarkers over time the anticipated number of measurements will be 40.

Pre-and post eGFR by creatinine, cystatin C will be compared by paired sample t-test (baseline vs. SVR12 measurement). Changes from baseline to all follow-up visits of the levels of all markers in **Table 1** will be assessed using a maximum-likelihood, mixed-effects repeated-measures model (MMRM) with all longitudinal observations included. The model will include terms for baseline and all subsequent visits (on-treatment, short-term and long-term follow-up). Means and 95% confidence intervals will be presented for change in markers from baseline through each follow-up visit. Analyses

will be performed using PROC MIXED with denominator degrees of freedom estimated by the Satterthwaite approximation. Covariance structure will be determined using the lowest Akaike information criterion. P values will be presented for each post-baseline visit as well as for all follow-up visits combined. In order to determine the kinetics of marker reduction, we will determine the average time in weeks until nadir. Outcomes will be checked for normality to meet the assumptions of parametric testing; appropriate transformations or non-parametric tests will be utilized. As an exploratory analysis, we will determine which pathway is the most influential on renal recovery. I will correlate improvements in eGFR and proteinuria with changes in novel biomarkers. I will evaluate the kinetics of improvement in these biomarkers as a recapitulation of the relative contributions of each. We expect an attenuated decline from baseline through each of the follow-up periods.

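### Section 3.7 fits the repeated-measures model to ten patients by maximum likelihood with Satterthwaite df: visit-level 95% intervals are 5–7% too narrow, and the undefined combined p-value may be strongly liberal

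*Combined protocol and SAP*

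**What the plan says.** Section 3.7 assesses change from baseline in all Table 1 markers with a "maximum-likelihood, mixed-effects repeated-measures model (MMRM) with all longitudinal observations included". It is run in PROC MIXED with "denominator degrees of freedom estimated by the Satterthwaite approximation. Covariance structure will be determined using the lowest Akaike information criterion". Two kinds of output are promised: "Means and 95% confidence intervals will be presented for change in markers from baseline through each follow-up visit", and "P values will be presented for each post-baseline visit as well as for all follow-up visits combined".

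The section does not mention REML, Kenward-Roger or any other small-sample correction. It does not list the covariance structures that AIC chooses among, give a fallback if a structure cannot be fitted, or define the combined test. Separately, eGFR "will be compared by paired sample t-test (baseline vs. SVR12 measurement").

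The visit schedule is in Section 3.6. Traditional markers (Table 1a): "Measured at Baseline, Week 4, Week 8, Week 12 or 16 (if needed), SVR4, SVR12, SVR24 and 1 year". Novel markers (Table 1b): "Measured at Baseline, Week 8, SVR12, and 1 year follow-up". Under the dosing regimen in the same section, non-cirrhotic treatment-naïve "patients will receive 8 weeks of Mavyret", so not every patient has an on-treatment week 12 visit.

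**The concern.** With ten patients, large-sample approximations have visible errors, and three choices in this model add to them.

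- Maximum likelihood underestimates the variance, and Satterthwaite df do not correct for that. The intervals therefore miss their stated 95% coverage.
- A joint F test with Satterthwaite df takes no account of how poorly a covariance matrix with many parameters is estimated from ten patients. An unstructured matrix has p(p+1)/2 parameters: 10, 28 or 36 for 4, 7 or 8 time points. AIC under maximum likelihood is quite willing to choose it.
- The combined p-value could be a joint F over all post-baseline visits, a joint F over the post-treatment visits only, or a one-df average change. These tests have very different error rates on the same data, and the plan leaves the choice open until the data are in hand.

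At stake is the planned inference for every traditional and novel marker in a study whose results are meant for publication.

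**Working it through.** **Inputs.** n = 10 patients (Section 3.7). Time points p: 4 in Table 1b, and 8 in Table 1a, or 7 without the optional week 12/16 visit. Two-sided 5% is assumed for tests, as no alpha is stated. The exact results assume complete data and one mean per visit, with baseline modelled as a visit.

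**The plan's own figure.** 10 patients × 4 measurements = 40, as stated. This fits Table 1b; the 8 visits of Table 1a would give 80 per marker.

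**Visit-level interval, unstructured covariance.** The maximum-likelihood variance is (n−1)/n = 9/10 of the unbiased one, so the SE ratio is √0.9 = 0.949. Satterthwaite df are 10 instead of 9.

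- Width ratio: 0.949 × 2.228 / 2.262 = 0.934.
- True error: the interval excludes zero when the paired t exceeds 0.949 × 2.228 = 2.114. On 9 df, 2·P(t > 2.114) = 0.0637, so coverage is 93.6%.
- A change with paired-t p = 0.064 would therefore be reported as p = 0.050.

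**Visit-level interval, compound symmetry.** Df are n(p−1) instead of (n−1)(p−1).

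- p = 4: 0.949 × 2.042 / 2.052 = 0.944.
- p = 7 or 8: 0.947.

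**Joint F over q = p−1 changes, unstructured covariance.** The exact reference is Hotelling's T². The error is P(F(q, 10−q) > (10−q)/9 × k × Fcrit), with k = 0.9 and Fcrit(q, 10) for maximum likelihood, and k = 1 and Fcrit(q, 9) for REML with Satterthwaite.

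| q | ML threshold | ML error | REML error |
|---|---|---|---|
| 3 | 7/9 × 0.9 × 3.708 = 2.596 | 13.5% | 10.4% |
| 6 | 4/9 × 0.9 × 3.217 = 1.287 | 42% | 36% |
| 7 | 3/9 × 0.9 × 3.135 = 0.941 | 58% | 52% |

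Under compound symmetry with maximum likelihood the joint error is only 7.0–8.0%.

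**With AIC selection (simulation).** The candidates are assumed to be compound symmetry, AR(1) and unstructured. The true covariance was compound symmetry (correlation 0.7), AR(1) (0.8), or random intercept plus exponential decay plus noise. There were 4,000 runs per cell, with complete data. Under maximum likelihood AIC chose the unstructured matrix in 16–17%, 26–32% and 41–48% of runs at 4, 7 and 8 time points.

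| Combined test | 4 points | 7 points | 8 points |
|---|---|---|---|
| Joint F, all post-baseline, ML | 11% | 21–24% | 32–37% |
| Joint F, post-treatment only, ML | 8–9% | 12–15% | 14–17% |
| Joint F, all post-baseline, REML with Satterthwaite | 7–8% | 13–16% | 21–25% |

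A one-df average change under maximum likelihood had 4.6–7.7% error across scenarios, and the single SVR12 comparison 5.9–7.4%. A second simulation of 1,500 runs per scenario, including a truth with unequal variances, gave a maximum-likelihood joint error of 9.8–11.0% at 4 points and 33–37% at 8.

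**Can the unstructured model be fitted?** With 8 time points, regressing the week 12/16 value on an intercept and the other 7 visits uses 8 coefficients. If 8 or fewer patients have that visit, the residual is zero, the likelihood is unbounded and the model cannot be fitted. With AIC then choosing only between compound symmetry and AR(1), the maximum-likelihood joint error is 8–11% at 7–8 time points.

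**The case against.** The part that follows from the text without further assumption is modest: about 6.4% error instead of 5% per visit, in an exploratory single-arm study of ten patients. It nearly vanishes if the authors wrote maximum likelihood loosely and will leave PROC MIXED at its REML default. The large figures need a joint F test, over all post-baseline visits, with AIC often choosing the unstructured matrix. Section 3.7 never says joint F, and its wording could equally mean one pooled change, whose error is near nominal. The 8-point figures assume all ten patients have the optional visit, which the 8-week regimen makes doubtful. Section 3.7 itself speaks of four measurements per patient, where the joint-F figure is 11%. The simulations depend on assumed structures and were coded in Python, not SAS.

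Much of this stands as a limit on size. The 8-point results are a full-attendance scenario, and all joint-F results are conditional. None of it removes the problem. The text says maximum likelihood and nothing elsewhere says REML. If REML was meant, a joint F is still liberal (13–16% at 7 points). That the combined test could be near nominal or several times too liberal is itself the reason to define it beforehand.

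**Conclusion.** The concern holds. With ten complete patients and baseline modelled as a visit, visit-level 95% intervals are 5.3–6.6% too narrow and cover about 93.6–93.7%. This is exact and needs no assumed SD or correlation. Fewer complete patients make it worse: 7.5% and 8.8% too narrow with 9 and 8 under the unstructured matrix. If baseline entered as a covariate at each visit, the shortfall with ten would be about 14% (ratio 0.864).

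The combined p-value is undefined. Its error is about 5–8% as a one-df average. As a joint F over all post-baseline visits it is about 11% for novel markers and 21–24% for traditional markers at 7 time points, given the assumed candidates and covariances. If the unstructured matrix cannot be fitted, the joint-F error at 7–8 points is 8–11%.

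This should be corrected before analysis. The interval shortfall is modest; the open definition of the combined test is the more serious part.

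**What to change.** In Section 3.7:

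1. Replace maximum likelihood with Satterthwaite df by REML with Kenward-Roger (DDFM=KR).
2. Name the structures that AIC compares, for example unstructured, AR(1) and compound symmetry. State that AIC chooses between AR(1) and compound symmetry if the unstructured model cannot be fitted. State how the week 12/16 visit enters the model. Do not fix compound symmetry alone: if the truth is AR(1), the average-change test then has 8.6–10.3% error even with REML and Kenward-Roger.
3. Define the combined p-value as a one-df contrast of the average post-baseline change, and list the visits it averages.

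In simulation the SVR12 error becomes 4.7–5.4% and the average-change error 3.5–5.2%. With the two-structure fallback they are 4.2–5.3% and 2.9–5.3%, so the average test can be somewhat conservative. For one-df tests most of the gain comes from REML. Kenward-Roger matters most if a joint F is kept: at 8 time points the REML error of 21–25% falls to 6.5–9%.

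The cost is SAP wording and SAS options. Intervals become about 7% wider under the unstructured matrix (1/0.934 = 1.07) and about 6% under compound symmetry (1/0.944 = 1.06). Some combined p-values will be less favourable, and a one-df average loses power if changes go in opposite directions at different visits.

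### If nadir means the lowest post-baseline value, average time to nadir is the same for a marker that never moves and one that falls at once and stays down, so it does not measure speed for a prompt response (minor)

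*Combined protocol and SAP*

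**What the plan says.** Section 3.7 gives one measure of how quickly markers respond: "In order to determine the kinetics of marker reduction, we will determine the average time in weeks until nadir". It has no rule on whether baseline is eligible, on a minimum fall, or on ties. It then proposes, as exploratory work, to use the kinetics of improvement to judge how much each biomarker contributes to renal recovery.

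The visits differ by marker set (section 3.6). Table 1a, traditional markers: "Measured at Baseline, Week 4, Week 8, Week 12 or 16 (if needed), SVR4, SVR12, SVR24 and 1 year". Table 1b, novel markers: "Measured at Baseline, Week 8, SVR12, and 1 year follow-up". The later visits are timed as "SVR12 (12 weeks after treatment ends), SVR24 (24 weeks after treatment ends) and 1 year follow-up (day 365"; SVR4 is 4 weeks after treatment ends. Course length varies by patient: some "noncirrhotic, treatment naïve patients will receive 8 weeks of Mavyret", and some who are "treatment experienced with either interferon and/or ribavirin will receive 16 weeks of Mavyret".

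The follow-up text in section 3.6 also says of all four post-treatment visits: "Kidney function tests and novel biomarker analysis will be assessed at each of these visits". A later sentence in the same paragraph limits the novel markers to SVR12 and 1 year.

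**The concern.** A time-to-nadir figure invites the reading that a smaller number means a faster response. The week of the lowest value depends only on how the eligible values rank against each other. Once a marker has fallen and levelled off, noise decides which later visit is lowest. A prompt, sustained fall is a plausible response to viral eradication, and for that shape the average nadir week says nothing about how fast the fall came.

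The risk is one of interpretation. A mean of 22 or 28 weeks could be reported as a decline lasting about half a year, or carried into the exploratory judgement of which biomarker contributes most.

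**Working it through.** **The plan's own figure.** Section 3.7 counts 10 patients × 4 measurements = 40. This reproduces and fits Table 1b (baseline plus three visits). Table 1a has eight visits on a 12-week course, which would give 80. The plan states no time-to-nadir figure.

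**Assumptions.** The 1-year visit is week 52 from first dose. Errors have unit within-patient SD and are independent unless stated. There are 10 patients.

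**Post-baseline visits, 12-week course.** SVR4, SVR12 and SVR24 fall at weeks 16, 24 and 36. Table 1a: 4, 8, 12, 16, 24, 36, 52. Table 1b: 8, 24, 52.

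**Step 1: the identity.** Subtracting a constant from every post-baseline value does not change which visit is lowest. A flat marker and one fully down by its first post-baseline visit and level afterwards therefore have the same nadir-time distribution, provided they share an error structure. Independence is not needed.

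**Step 2: the common value.** With exchangeable errors each of k visits is lowest with probability 1/k, so the expected nadir week is the plain mean of the visit weeks.
- Table 1a: 152/7 = 21.7 weeks (21.3 to 24.0 across 8- to 16-week courses).
- Table 1b: 84/3 = 28.0 weeks (26.7 to 29.3). With novel markers at all four post-treatment visits: 136/5 = 27.2.
- Errors correlated as exp(−gap/12 weeks), by simulation: about 25 and 28.6, again equal for the flat and the prompt marker.

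**Step 3: baseline eligible, counted as week 0.**
- Flat: 152/8 = 19.0 (Table 1a); 84/4 = 21.0 (Table 1b).
- Immediate 2-SD fall, simulated: 21.7 and 27.7.

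The two now differ, but the responding marker has the later nadir. The 10-patient confidence interval excludes the flat value in only 6% (Table 1a) and 15% (Table 1b) of simulated trials.

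**Step 4: other 2-SD shapes, post-baseline nadir.**

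| Shape | Table 1a (weeks) | Table 1b (weeks) |
|---|---|---|
| Half-life 1 week | 22.2 | 28.1 |
| Half-life 4 weeks | 26.8 | 32.0 |
| Linear over 52 weeks | 38.1 | 43.0 |
| Fall by week 8, then rebound | 13.6 | 14.4 |

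So the statistic does respond to slow decline and to rebound. Its confidence interval excludes the flat value in 79% and 71% of trials for the linear fall, and in 76% and 87% for the rebound.

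A mean near 22 to 28 weeks does not identify one shape. If half the patients fall linearly and half rebound, the means are (38.1 + 13.6)/2 = 25.9 and (43.0 + 14.4)/2 = 28.7. One patient's nadir week has SD 15.8 (Table 1a) or 18.2 (Table 1b), so the half-width at n = 10 is 2.262 × 15.8/√10 = 11.3 weeks, or 13.0.

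**Step 5: a flat marker in Table 1a v Table 1b, 12-week course.**
- Post-baseline, exchangeable: 28.0 − 21.7 = 6.3 weeks (27.2 − 21.7 = 5.5 with all four post-treatment visits).
- Post-baseline, correlated: about 3.5.
- Baseline eligible, exchangeable: 21.0 − 19.0 = 2.0.
- Baseline eligible, correlated: about 0.2.

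**Step 6: mixed-model contrasts.** Approximated as paired differences with 9 degrees of freedom, the 95% half-width is 2.262 × √(2/10) = 1.01 SD. Noncentral-t power is:
- week-8 change, 2-SD immediate fall: 97.7%;
- 1 year minus week 8, linear 2-SD fall (2 × 44/52 = 1.69 SD): 91.9%;
- 1 year minus week 8, full 2-SD rebound: 97.7%;
- SVR12 minus week 8, linear fall (2 × 16/52 = 0.62 SD): 23.4%.

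**The case against.** The strongest reply is that the plan speaks of marker reduction, so time to nadir presupposes a fall, and the fall itself is tested elsewhere: "Means and 95% confidence intervals will be presented for change in markers from baseline through each follow-up visit", with p values for each visit. On that view nadir week is an undefined term in a descriptive summary of a 10-patient, single-arm study. Much of this stands. It is why the point is minor, and why the confusion with a flat marker matters less once the visit means are read first. It does not rescue the figure as a measure of speed. For a marker known to have fallen promptly and stayed down, the average nadir week still reflects when visits were scheduled.

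A reader might infer that the plan sets out to compare nadir weeks between Table 1a and Table 1b, and that such a comparison is always off by about 6 weeks. The documents support neither. Section 3.7 proposes no such comparison, and its sentence on relative contributions most naturally refers to the novel markers, which share one schedule. Nor does it say that nadir week is the measure used there. The 6.3-week gap needs both exchangeable errors and a post-baseline nadir.

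A reader might also infer that a value near 22 or 28 weeks shows an early plateau. It does not, because mixtures of other shapes give the same values.

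The novel-marker visit discrepancy is editorial. Table 1b, the later follow-up sentence and the four-measurement count all agree, and one sentence departs from them.

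**Conclusion.** The concern holds as a minor point about the choice of summary. With a post-baseline nadir, the equality between a flat marker and an immediate, sustained fall is exact under any shared error structure. The values 21.7 and 28.0 weeks are less firm: they assume a 12-week course, the 1-year visit at week 52 from first dose, and exchangeable errors. Counting baseline as a possible nadir makes the flat marker look faster, so neither reading measures the speed of a prompt response.

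A flat marker would differ between the two tables by about 0.2 to 6.3 weeks from the schedule alone, depending on error correlation and on whether baseline counts. This matters only if someone makes that comparison. The use is exploratory and no decision depends on it.

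**What to change.** In section 3.7:

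1. Report kinetics as mixed-model estimates with 95% confidence intervals: the already planned change from baseline at week 8 (and at week 4 for Table 1a), plus one added contrast, 1 year minus week 8. SVR12 minus week 8 may be shown descriptively, given its low power for a slow fall.
2. Interpret the estimates and intervals directly. Do not sort markers into response categories by non-significance. State that the half-width is about 1.0 within-patient SD at n = 10 with independent errors, so an interval covering zero does not show that there was no later change.
3. Keep time to nadir as a descriptive figure only, defined from post-baseline visits and given only for markers whose mixed model shows a fall.
4. Compare novel with traditional markers only at shared visits: baseline, week 8, SVR12 and 1 year.

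Separately, in section 3.6, reconcile the sentence placing novel-marker analysis at every post-treatment visit with Table 1b, the later follow-up sentence and the four-measurement count in section 3.7.

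The cost is wording and one contrast, with no new samples or visits. The weeks-to-nadir figure loses its main role, and the contrasts that replace it are wide with 10 patients.
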